3.3. Setting/context

Adult general critical care units, cardiothoracic critical care units and acute hospitals in England and Wales.

3.4. Data sources

The study will utilise data collected for the CMP and NCAA. The CMP has been established for 20 years and the resulting high-quality clinical database (of over 1.5 million critical care admissions) has underpinned evaluations of policy and practice in critical care. NCAA was established in 2009 as a joint venture between ICNARC and the Resuscitation Council (UK). Data for both audits are collected to precise rules and definitions by trained data collectors and undergo extensive validation, both locally and centrally, for completeness, logicality and consistency. The CMP database has been independently assessed and scored highly by the Directory of Clinical Databases (DoCDat) against their ten domains (describing elements of coverage and accuracy). Similar processes for NCAA were developed building on the knowledge and experience of the successful systems in place for the CMP.

Data from the CMP will be linked with high quality clinical data collected for the National Diabetes Audit, UK Renal Registry and National Adult Cardiac Surgery Audit. Taken together with the CMP and NCAA, these five national clinical audits hold a combined total of over 80 years' experience of managing and reporting on patients' data to improve outcomes in their respective fields.

The National Diabetes Audit (http://www.hscic.gov.uk/nda) is the largest annual clinical audit in the world and is managed by the Health and Social Care Information Centre (HSCIC) working with Diabetes UK and the National Cardiovascular Intelligence Network, Public Health England. The National Diabetes Core audit, covering care processes, treatment targets, complications and mortality for people with diabetes in primary care and specialist services, is now in its ninth year.

Over recent years, the audit has included over 80% of people diagnosed with diabetes in England and Wales.

The UK Renal Registry (http://www.renalreg.com/) was established by the Renal Association and provides a focus for the collection and analysis of standardised data relating to the incidence, clinical management and outcome of end-stage renal disease. The Registry has been in operation since 1995, with 100% coverage of adult renal units in England and Wales since 2007.

The National Adult Cardiac Surgery Audit (http://www.ucl.ac.uk/nicor/audits/Adultcardiacsurgery) collects consecutive operation data from all 35 NHS hospitals in the UK that carry out adult heart surgery. It has been running since 1977, making it the longest running of all UK national clinical audits. The audit is managed by the National Institute for Cardiovascular Outcomes Research (NICOR) at University College London, in association with the Society for Cardiothoracic Surgeons.

4. Data linkage and data management

4.1. Data linkage

Data linkage will be undertaken by the HSCIC Data Linkage and Extract Service (DLES) acting as a 'trusted third party' (see: Study flow diagram). Identifiers (with no associated clinical data) will be uploaded from each national clinical audit to secure servers at HSCIC. DLES will perform the data linkage and will return to each national clinical audit their local identifier (a field that uniquely identifies records within that dataset) together with a common key that can be used to link all records of the same patient across the different datasets. The three national clinical audits external to ICNARC will then transfer to ICNARC an agreed pseudonymised dataset (including the common key) for records that were successfully linked (see Appendix 1). Similarly, DLES will perform a pseudonymised data extract from HES and ONS data and pass these datasets (again including the common key) to ICNARC. ICNARC will produce pseudonymised data extracts from the CMP and NCAA and these will be linked to the datasets provided by the national clinical audits and DLES using the common key. In this way, only pseudonymised data will be linked between the multiple data sources.

Each data provider will retain the files linking their local identifier to the common key to facilitate future research using linked datasets, subject to necessary approvals.

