5.2. Model specification

5.2.1. Risk models for adult general critical care (objective 1)

5.2.1.1. Mortality at 30-days, 90-days and 1-year and time to death (objective 1a)

Outcome defined as death (from any cause) within 30-days, 90-days or 1-year of admission to the critical care unit and number of days from admission to death, established by data linkage with death registrations from ONS.

Patients included in the models will be all those admitted to a critical care unit and discharged alive from the critical care unit.

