5.2.1.2. New diagnosis of diabetes post-critical care (objective 1b)

Outcome defined as recording of the patient in the National Diabetes Audit database with a year of diagnosis in the calendar year after discharge .

Patients included in the model will be all those discharged alive from acute hospital following a critical care unit admission, excluding any with a pre-existing diagnosis of diabetes (as identified from data linkage with earlier years of data from the National Diabetes Audit, diagnostic coding within HES, or by recording of a primary or secondary reason for admission to the critical care unit associated with diabetes, e.g. diabetic ketoacidosis), those registered with a GP practice that did not submit data to the National Diabetes Audit in the subsequent year, and those in whom diabetes is diagnosed shortly after the episode of critical care

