5.2.1.3. New diagnosis of end-stage renal disease post-critical care (objective 1c)

Outcome defined as recording of the patient in the UK Renal Registry database with a date of diagnosis of end-stage renal disease within one year following the date of discharge from hospital.

Patients included in the model will be all those discharged alive from acute hospital following a critical care unit admission, excluding any with a pre-existing diagnosis of end-stage renal disease as identified from data linkage with earlier years of data from the UK Renal Registry or by recording of an ongoing requirement for renal replacement therapy for irreversible end-stage renal disease in the CMP database

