Appendix 2 Approach to model development

For each newly developed or revised risk prediction model, we fill adopt the following general approach to model development.

- 1. Potential predictors will be identified and patterns of missing data within the potential predictors will be explored, with particular attention to the completeness and accuracy of data linkage between the databases. Approaches to handling the missing data will be compared, based on the best performing approaches from previous work.
- The most appropriate functional form for each potential predictor will be explored, taking
 into consideration the use of continuous non-linear models (e.g. restricted cubic splines or
 right-restricted cubic splines) for continuous predictors and appropriate categorisation and
 structure of categorical predictors.
- 3. A main effects model will be fitted through a process of deleting terms, re-fitting and verifying, using: likelihood ratio tests to remove non-significant predictors; and the Bayesian Information Criterion (BIC)^[30] as the basis to determine which predictors make an important contribution to the fit of the model.
- 4. The functional form of each predictor included in the main effects model will then be reexamined to confirm if any changes are required based on adjustment for other important predictors.
- 5. Finally, interactions between the predictors will be introduced based on clinical input to identify and prioritise the potentially important interactions to consider and avoid over fitting, with interactions retained if they have a positive effect on the BIC.

For objectives 2a and 3a: the addition of new predictors to existing models will be considered and then the effect of those predictors previously included in the risk model will be re-assessed to determine whether they still make an important contribution to the model (see above).

For objectives 2b and 3b: the risk model will be re-fitted to the new outcome, predictors that were previously considered but were found not to be important predictors for hospital survival will be reassessed by adding them to the model and finally the effect of those predictors previously included in the risk model will be re-assessed to determine whether they still make an important contribution to the model (see above).

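### For outcomes found by linkage, the protocol sets no traceability criterion, so as written a failed link counts as no event

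*Protocol*

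**What the plan says.** Section 4.1 describes the data flow. The linkage service returns each audit's local identifier "together with a common key that can be used to link all records of the same patient across the different datasets". The National Diabetes Audit, UK Renal Registry and National Adult Cardiac Surgery Audit then "transfer to ICNARC an agreed pseudonymised dataset (including the common key) for records that were successfully linked". HES and ONS extracts come separately from the linkage service. The section does not say whether a CMP or NCAA record that cannot be traced still receives a key, or is flagged.

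Section 5.2 sets outcomes and populations:

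- **1a:** death is "established by data linkage with death registrations from ONS". The population is wide: "Patients included in the models will be all those admitted to a critical care unit and discharged alive from the critical care unit".
- **1b:** "Outcome defined as recording of the patient in the National Diabetes Audit database with a year of diagnosis in the calendar year after discharge". The population is everyone discharged alive from acute hospital, less those with prior diabetes, those diagnosed shortly after critical care, and those whose GP practice did not submit to the diabetes audit.
- **1c:** "Outcome defined as recording of the patient in the UK Renal Registry database", dated within a year of hospital discharge. The only exclusion is existing end-stage renal disease.
- **2b and 3b:** date of death from ONS linkage, in all admissions to participating cardiothoracic units and all eligible arrests respectively.
- **3c:** critical care days from linkage of NCAA to CMP.
- **1d, 2c and 3d:** index-stay days from the audit itself, later days from HES.

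None of the stated populations requires a successful trace (1d states no population). Appendix 2, step 1, promises to examine missing data in potential predictors "with particular attention to the completeness and accuracy of data linkage between the databases". Appendix 1 lists no trace or match-status field in any extract.

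**The concern.** When an outcome is defined by a record being present, its absence can mean two things: the patient was traced and had no event, or the patient could not be traced. A missing predictor shows up as missing; a missing outcome record of this kind shows up as a zero. With populations of all eligible patients, the second group enters the denominator and cannot enter the numerator.

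The models are meant for comparative reporting between providers (objective 4a), and section 5.1.1 includes the SMR among the performance measures. If identifier quality differs between units, a unit with more untraceable patients would appear to have fewer late deaths, new diagnoses and later admissions than it had. Predictors that go with poor identification would look protective. Whether linkage does differ in this way is not stated in the protocol; it is a possibility to be checked.

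**Working it through.** **1. Do the planned denominators allow for linkage loss?** The inputs are in section 3.2 and the synopsis. For objective 2, admissions minus deaths gives 34,000 − 3,000 = 31,000 for development and 2,300 − 200 = 2,100 for validation. Both equal the survivor counts in the synopsis, so nothing has been deducted for failed linkage. These may simply be pre-linkage counts, and are not wrong as such.

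**2. Dilution of a wholly linkage-dependent outcome (1b, 1c).** Let p be the true risk and u the unlinkable share, unrelated to risk. If unlinked patients count as event-free, observed risk = p(1 − u). The protocol gives neither figure, so p = 10% and u = 1% to 10% are assumptions.

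| u | Observed risk when p = 10% |
|---|---|
| 1% | 0.10 × 0.99 = 9.9% |
| 2% | 0.10 × 0.98 = 9.8% |
| 5% | 0.10 × 0.95 = 9.5% |
| 10% | 0.10 × 0.90 = 9.0% |

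**3. Effect on a unit comparison.** For a unit whose true observed-to-expected ratio is 1, the apparent ratio is (1 − u in the unit) / (1 − u on average). With an assumed 10% in the unit:

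- average 3%: 0.90 / 0.97 = 0.93;
- average 2%: 0.90 / 0.98 = 0.92.

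These apply where every event depends on linkage.

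**4. Effect on all-cause mortality.** Appendix 1 lists date of death and hospital discharge status in both CMP and NCAA, so in-hospital deaths are known without ONS. Only post-discharge deaths are diluted: observed deaths = in-hospital deaths + post-discharge deaths × (1 − u).

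Take 3b as an example. Section 3.2 gives 56,000 arrests and 10,000 survivors. Reading these as hospital survivors, and taking all in-hospital deaths as falling within the year, leaves 56,000 − 10,000 = 46,000 known deaths. Assume 30% of survivors die later within the year, that is 3,000:

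- at u = 10%: 46,000 + 3,000 × 0.90 = 48,700;
- at u = 3%: 46,000 + 3,000 × 0.97 = 48,910;
- ratio: 48,700 / 48,910 = 0.996.

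The contrast that gives 0.93 for a wholly linked outcome almost vanishes here. 1a and 2b lie somewhere between, depending on the proportion of deaths that follow hospital discharge.

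**5. Sample lost by restricting to traceable patients.** From the 280,000 unit survivors for model fitting in section 3.2: 2,800 at 1%, 5,600 at 2%, 14,000 at 5% and 28,000 at 10%. From 31,000 cardiothoracic unit survivors: 310, 620, 1,550 and 3,100.

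**The case against.** The strongest reply is that the protocol is silent on unlinked patients and does not prescribe that they be scored event-free. Handling them is ordinary analysis-plan content, and section 5.1.4 says the analysis plans will be finalised before modelling. This stands in part: no rule either retains or excludes such patients. But the population and outcome definitions are set in section 5.2, and applied together they produce the misclassification. Appendix 1 also fixes the fields to be requested, which a later analysis plan cannot easily extend.

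A reader might infer that untraced and event-free patients can never be separated. The documents do not support that. The common key is a field in both the CMP and NCAA extracts, and its absence might mark an untraced record. Every patient also had an index hospital stay, so a missing index spell in HES, where HES covers the hospital, would signal a failed link. The protocol assigns neither of them this use.

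A reader might also infer that every model is affected, or that untraced patients would all be counted as alive. Neither holds. Outcomes 2a and 3a come from CMP and NCAA, in-hospital deaths and index-stay days are in the audits, and the rule on sending only linked records concerns the three external audits, not ONS or HES.

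Two safeguards deserve credit. The 1b exclusion of non-submitting GP practices shows that the authors separate not ascertainable from no event, but it addresses source coverage, not failed linkage. It also relies on a GP practice code that Appendix 1 lists only under HES. The linkage check in Appendix 2 is real, but is placed under missing predictors.

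Finally, section 3.4 describes extensive validation of both audits, so the unlinkable share may be small. The figures used here are assumed.

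**Conclusion.** The point holds for outcomes ascertained by linkage: 1b and 1c in full; post-discharge deaths in 1a, 2b and 3b; critical care days in 3c; and later hospital days in 1d, 2c and 3d. For these, the definitions taken literally turn failed linkage into no event, and no stated criterion prevents it.

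For 1b and 1c, the loss is roughly proportional to the unlinkable share. A unit ratio of about 0.93 under identical care is an illustration at 10% against 3% unlinkable, and an upper bound on the distortion for mortality under that contrast; for 3b the same contrast gives about 0.996. All of this assumes that linkage failure is unrelated to risk and that unlinked patients are counted as event-free. The distortion between providers further requires that linkage varies by unit. The protocol's figures establish neither the unlinkable share nor that variation.

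**What to change.** - **Section 4.1 and Appendix 1:** request a trace or match-status indicator for every CMP and NCAA record submitted, including those matched in no source. Alternatively, state that absence of a common key, or of the index HES spell where HES covers the hospital, marks a record as untraced.
- **Section 5.2:** restrict each model with a linked outcome to traceable patients. Apply this regardless of known in-hospital outcome; otherwise untraced patients would be kept only when they died, which introduces a new bias. In time-to-death models, untraced patients may instead be censored at hospital discharge.
- **Reporting:** give linkage rates and the characteristics of traced and untraced patients by unit or hospital.

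The cost is one field or one defining sentence in the linkage request, an eligibility sentence in section 5.2, a small loss of sample (at an assumed 5%, 14,000 of 280,000, leaving 266,000) and some loss of representativeness, which the traced-versus-untraced comparison would show. It is cheapest if settled before the linkage request is submitted.

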4.2. Data management

The data for this study will be handled under the same security arrangements as for patient identifiable data from the CMP and NCAA. All data will be managed in accordance with ICNARC's Information Security Policy.

Datasets resulting from the linkage process will be stored on secure servers at ICNARC. No identifiable information will be recorded and only the staff involved in the Study will have acces to the datasets.

5. Statistics and data analysis

5.1. Description of statistical methods

5.1.1. Assessing the predictive performance

Throughout the study, risk prediction models will be validated for their discrimination, calibration and overall fit. The following panel of measures will be used to give an overall assessment of model performance.

The discrimination of the model will be estimated by the *c* index (equivalent to the area under the receiver operating characteristic curve) ^[19, 20] and accuracy will be assessed by Brier's score (mean squared error between outcome and prediction) ^[21, 22] We will assess calibration graphically with predicted probability on the X-axis and the observed outcomes on the Y-axis in 10 equal-sized risk groups (calibration plot) and by Cox's calibration regression (linear recalibration of the predicted log odds) ^[23]. The standardised mortality ratio (SMR) with 95% confidence interval (CI) will be calculated to observe the difference between actual and expected mortality by dividing the observed number number of deaths by the number of deaths predicted by the model. Because of the size of the datasets to be used, we will not assess the calibration of the model with the Hosmer-Lemeshow c-statistic because this may lead to misleading conclusions ^[24].

5.1.2. Internal and external validation

Each newly developed or revised risk prediction model will be validated using the above measures both within the development sample and in independent validation data.

Where a prognostic model is based on a very large sample size and relevant variables are included in the final model, optimism is small and so, the apparent estimates of model performance (*c* index and Brier's score in the development data) are attractive because of their stability^[25]. However, to assess optimistic performance within the development data, the percentage of over-fitting will be estimated by the optimism-corrected statistics.

Where existing risk prediction models are modified, the performance of the revised model will be compared with the existing model using reclassification techniques. The improvement in reclassification will be quantified as the Net Reclassification Improvement NRI. We will calculate the NRI both using pre-defined categories of risk and also as a continuous measure (i.e. the proportion with any improvement in predicted risk compared against the proportion with any worsening in predicted risk).

After one year, the data linkage will be updated to provide an additional year of data to serve as independent validation data.

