5.1.4. Analysis of outcome measures

The analysis plans will be finalised with input from the Clinical Advisory Groups prior to modelling.

The following approaches for model development will be applied depending on the outcome and objectives of the analysis:

- To model mortality at fixed time-points (hospital discharge, 30 days, 90 days, 1 year), ROSC greater than 20 minutes and hospital survival: logistic regression (including, if appropriate, random effects of critical care unit/hospital).
- To model time-to-event outcomes: standard survival regression methods such as Weibull and Cox regression.
- To handle interval-censored data: Cox proportional hazards models,^[28] complementary loglog models using partial likelihood estimation (to permit interval censoring) and discretetime hazard models.^[29]
- To account for both interval censoring of the time-to-onset and competition with death: cause-specific Cox proportional hazards models [30] and illness-death models will be considered. [31]
- To model critical care/hospital resource use and costs: multilevel regression models and loglinear regression models.

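### In the development sample, the SMR and Cox calibration regression of an ordinary logistic model equal their ideal values by construction, so they cannot serve as internal validation

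*Protocol*

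**What the plan says.** Protocol 5.1.1 sets one panel of measures: the c index, Brier's score, a plot of "observed outcomes on the Y-axis in 10 equal-sized risk groups (calibration plot"), calibration "by Cox's calibration regression (linear recalibration of the predicted log odds"), and the SMR: "The standardised mortality ratio (SMR) with 95% confidence interval (CI) will be calculated to observe the difference between actual and expected mortality". The Hosmer-Lemeshow statistic is deliberately left out.

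Protocol 5.1.2 then states that each new or revised model "will be validated using the above measures both within the development sample and in independent validation data". It exempts no measure from the development sample. It goes on to argue that in very large samples "the apparent estimates of model performance (*c* index and Brier's score in the development data) are attractive because of their stability", and adds that "the percentage of over-fitting will be estimated by the optimism-corrected statistics", without naming the statistics to be corrected. An additional linked year supplies the independent data.

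Protocol 5.1.4 plans, for mortality at fixed time-points, ROSC and hospital survival, "logistic regression (including, if appropriate, random effects of critical care unit/hospital").

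**The concern.** With Hosmer-Lemeshow excluded, the SMR and Cox regression are the only numerical measures in the panel that are specific to calibration. Brier's score mixes calibration with discrimination. In the data used for fitting, an ordinary logistic model gives the ideal value of both measures whatever its quality.

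A report that followed 5.1.2 literally could therefore list an SMR of 1.00 and a slope of 1.00 for each such model under internal validation. The SMR would carry a confidence interval that looks like a test passed. With the 3,000 deaths given for objective 2, a simple Poisson interval would be about 1 ± 1.96/√3,000 = 1 ± 0.036. Readers of the provider comparisons planned under objective 4a could take these figures as evidence.

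The point matters most for cardiothoracic care, where Protocol 3.2 expects only 200 deaths in the independent data. The same approximation gives ± 1.96/√200 = ± 0.14 on the SMR there, so informative internal evidence would be useful.

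**Working it through.** The protocol gives no figure to reproduce. The check is algebraic, followed by simulation. Effect sizes, numbers of predictors and between-unit SDs in the simulations are assumptions.

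**Algebra.** Let y be the outcome (0 or 1), p the fitted probability, x the predictors including the constant, and lp = x'b the fitted log odds. Maximum likelihood solves Σ x(y − p) = 0.

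1. The row for the constant gives Σy = Σp, so SMR = Σy/Σp = 1.
2. Weighting the rows by b gives Σ lp(y − p) = 0. Cox's regression fits logit = α + β·lp, and its two equations are Σ(y − q) = 0 and Σ lp(y − q) = 0, where q is the recalibrated probability. At α = 0 and β = 1, q = p and both hold. The log likelihood is concave, so this is the solution.
3. The row for any category entered as a main effect gives SMR = 1 within that category. Splitting the development sample by a modelled factor does not help.

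**Fixed-effects models.** Development n = 34,000 (Protocol 3.2, objective 2). The stated death rate is 3,000/34,000 = 8.8%; the simulated rate was 7.6%. The misspecified model omits a quadratic term and an interaction.

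| Setting | SMR | Intercept | Slope | c |
|---|---|---|---|---|
| Misspecified model, development data | 1.000 | 0.000 | 1.000 | 0.76 |
| Pure-noise model, development data | 1.000 | 0.000 | 1.000 | 0.52 |
| Misspecified model, new data (n = 2,300, log odds raised by 0.3) | 1.16 | −0.19 | 0.83 | 0.71 |

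In the misspecified model, observed/expected deaths over the ten development risk groups, from lowest to highest risk, were 1.95, 1.49, 1.10, 1.09, 1.06, 0.91, 0.84, 0.93, 0.84 and 1.08. The calibration plot reveals the fault that the SMR and Cox regression miss.

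**Random-intercept models**, correctly specified, evaluated in their own fitting data:

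| Assumed between-unit SD | Fixed-part SMR / slope | Marginal SMR / slope |
|---|---|---|
| 0.3 | 1.03 / 0.99 | 1.013 / 1.002 |
| 0.5 | 1.07 / 0.97 | 1.006 / 1.002 |
| 0.8 | 1.15 / 0.91 | 0.998 / 0.995 |

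The identity nearly survives with marginal predictions and fails with fixed-part predictions. As these models were correctly specified, the fixed-part departures do not signal poor fit.

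**Optimism correction.** 40 bootstrap models with 20 predictors, each evaluated on the original sample:

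| n | Slope | Intercept | SMR |
|---|---|---|---|
| 34,000 | 0.99 | −0.03 | 0.996 |
| 3,400 | 0.93 | −0.16 | 1.001 |
| 340 | 0.48 | −1.06 | 1.015 |

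Correction frees the slope and intercept. The SMR stays near 1 even at n = 340, so it becomes informative only in data that played no part in the fit.

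**The case against.** A reader might infer that the whole development-sample half of the validation is empty. The protocol does not support that. The c index, Brier's score and calibration plot belong to the same panel and are not forced; the plot exposed the misspecified model above, and a c index of 0.52 exposed the noise model.

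A reader might also infer that calibration goes untested or that serious over-fitting would be hidden. Neither follows. The independent year applies the same measures to new data, Protocol 3.2 links six years of CMP data partly to examine fit over time, and 5.1.2 already plans optimism correction. It defends apparent values only for the c index and Brier's score, and no decision rule rests on the development SMR or slope. Harsher assumptions (11,300 admissions, 20 true and 60 noise predictors, no selection) give a mean new-data slope of about 0.87. However, they apply to objective 2 a two-year restriction that 3.2 states in its general critical care paragraph, and they ignore the deletion and BIC steps of Appendix 2.

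It can fairly be added that the list of corrected statistics is detail for an analysis plan, and that bootstrap correction is imperfect: in an all-noise model with 80 predictors the corrected slope was 0.49 against about 0 in new data.

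All of this limits the consequence. It does not rescue the sentence in 5.1.2, which prescribes two measures where, for ordinary logistic models, they cannot respond to the quality of the model.

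**Conclusion.** The point holds in a narrow form. For maximum-likelihood logistic models with an intercept and no random effects, the apparent SMR and apparent Cox regression are fixed at 1, 0 and 1 in the development sample and validate nothing. With multiple imputation or marginal random-effects predictions this is approximately true. With fixed-part random-effects predictions it is not true. The algebra concerns the logistic models only, not the time-to-event or resource-use models.

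The practical size is modest. Over-fitting is likely to be small at the planned sample sizes: a corrected slope of about 0.99 at 34,000 records, assuming 20 predictors and no selection. The 330,000 admissions used to fit the general critical care models should leave less still. The harm is false reassurance from two reported figures. The planned external validation remains sound.

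**What to change.** Amend Protocol 5.1.2 as follows.

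- State that the apparent SMR and apparent Cox regression in the development sample are not used as validation. Keep the c index, Brier's score and calibration plot there.
- State that the optimism-corrected statistics include the calibration slope and intercept, with the Appendix 2 selection steps repeated in each resample.
- Report the SMR and Cox regression only in data not used to fit the model: the independent year and, where useful, left-out years or linked years outside the fitting period. For objective 1 the latter amount to about 850,000 − 330,000 = 520,000 admissions.
- Treat leave-one-unit-out results as optional and read them with care. They also reflect real differences between units, which these models exist to measure, and objective 2 has only eight units.

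No new data are needed, since Appendix 1 already lists the dates and the unit and hospital identifiers. The cost is a short wording change, extra computing, and internal calibration that looks slightly less perfect.
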